10	Data Management.....	12

11	Amendments to the RSP	13
12	Deviations from the RSP	13
13	Device accountability	13
14	Statements of compliance	13
14.1	Declaration of Helsinki and compliance with standards.....	13
14.2	Ethics Committee Approval.....	13
14.3	Audits and Supervision	13
14.4	Study Records	14
15	Informed consent process	14
15.1	Obtaining informed consent.....	14
15.2	Data Privacy.....	14
16	Incident reporting	15
16.1	Incident Reporting.....	15
16.2	Definition of Incident	15
16.3	Reporting process.....	15
17	Suspension or premature termination	15
18	Publication Policy	16
19	Bibliography	16
20	Revision History	16
21	Appendix I: List of Investigators	17

Signature Page

By signing this page the Sponsor, Coordinating Investigator and Principal Investigator agree to conduct this investigation in accordance with the current investigational plan. No changes to this clinical investigation plan will be permitted without the written approval of both parties. If substantial amendments to this plan become necessary, written approval by the Ethics Committee will be obtained before the changes are clinically implemented, except under emergency circumstances to protect the rights, safety and well-being of the subjects.

Sponsor Signature

_____
PRINT NAME_____
DATE_____
SIGNATURE

TITLE

Coordinating Investigator Signature

PRINT NAME_____
DATE_____
SIGNATURE_____
Coordinating Investigator_____
TITLE

Principal Investigator Signature

PRINT NAME_____
DATE_____
SIGNATURE_____
Principal Investigator_____
TITLE

1 Clinical Investigation Synopsis

Name of device	Commercially available Cochlear™ Nucleus® Profile with Slim Modiolar Electrode (CI532)
Short study title and study number:	CEL5661: Retrospective CI532 Hearing Performance
Principal Investigator (s)	Please refer to Appendix I
Coordinating Investigator	[REDACTED]
Start date	March 2017
End date	November 2018
Total expected duration of the retrospective study:	21 months
Study design:	Multicenter retrospective data collection of already available routine clinical data.
Number of datasets:	≥ 150 datasets
Inclusion criteria:	
 1. Ability to conduct adult hearing performance test material 2. Good German language skills to assess clinical hearing performance 3. All CI532 recipients assessed via routine clinical measurements at pre implant, and post implant intervals with available data records in hospital files. 4. Patients that have read understood and signed the PIC.
Exclusion criteria:	
 1. Recipients that have participated in the CLTD5446 study.
Primary objectives:	
 1. To assess available speech understanding in quiet and in noise pre-operative (daily listening condition) and at 6 months post CI532 implantation (best aided conditions)
Secondary objectives:	
 1. To compare available aided (daily listening condition) and unaided pure tone audiometric thresholds obtained before surgery and at 6 months after CI532 surgery 2. To get insight for available CI532 device characteristics (electrode impedances, NRT, MAP T and C levels) and patient characteristics (datalogging) (cdx files) 3. To assess subjective surgeon's opinion and clinical experience with CI532 via a questionnaire

Primary endpoints:	
 1. Change from pre-op (daily listening condition) baseline speech understanding in quiet and in noise at 6 months post-op (best aided conditions) 2. The proportion of the recipient cohort in percent examined showing post-operative improvement per test and listening condition.
Secondary endpoints:	
 1. Change from pre-op baseline aided (daily listening condition) and unaided thresholds at 6 months post-operative 2. Defined normative CI532 device characteristics (electrode impedances, NRT, MAP T and C levels) and patient characteristics (datalogging) 3. Combined subjective clinical experience and opinion about CI532 from surgeons

2 Terms and Abbreviations

Abbreviation	Definition
CI532	Cochlear™ Nucleus® Profile with Slim Modiolar Electrode
RSP	Retrospective Study Plan
NRT	Neural Response Telemetry
MAP T&C levels	Subjective threshold (T) or comfortable (C) level for an electrode measured in current level units.
cdx	computer record files
CRF	Case Report Form
PIC	Patient Informed Consent
CI	Cochlear implants
PMS	Post-market Surveillance
ENT	Ear Nose Throat
OLSA	Oldenburger Sentence Test
HSM	Hochmayer Schulz Moser Sentence Test
SNR	Signal to Noise Ratio
SRT	Speech Reception Threshold
EC	Ethic committee
NCA	National Competent Authority
CE	Conformité Européene = European Conformity
ID	Identification

3 Introduction

Cochlear implants (CI) restore auditory sensitivity in the case of moderate to profound levels of sensorineural hearing loss. Typically patients implanted with cochlear implants can achieve a relatively high level of speech understanding in quiet and to a lesser degree in background noise. In general performance is sufficiently high that currently for cochlear implantation in many countries the criterion is for pre-operative speech recognition scores, measured in quiet, to be inferior or equal to 50% correct using well fitted acoustic hearing aids.

The CE marked Cochlear™ Nucleus® Profile with Slim Modiolar Electrode (CI532) has a perimodiolar (pre-curved) design and is designed to bring electrode contacts closer to the medial wall of the cochlea and so therefore closer to the spiral ganglion. This could potentially improve the hearing performance.

This investigation aims to retrospectively collect hearing performance data that have been measured by five clinics in Germany as part of their clinical routine in CI532 recipients. This will allow the combination of post market follow-up hearing performance data within the same language group to be used as bench mark data.

4 Identification and description of the commercially available CI532

The **CE marked CI532** is manufactured at Cochlear Limited in Australia. The CI532 is commercially available as a state of the art treatment for moderately severe to profound levels of sensorineural hearing loss within the clinical routine.

Please refer to the commercially available brochures; manuals and labelling in German language for identification and description of the commercially available CI532:

- Nucleus® Cochlea-Implantate - Wichtige Informationen für Cochlea-Implantatträger
- Nucleus® CI532 Cochlea-Implantat mit Slim-Modiolar-Elektrode - Handbuch für Ärzte
- Nucleus® CI532 Cochlea-Implantat mit Slim-Modiolar-Elektrode – Dokumentation
- Cochlear™ Nucleus® Weltweit eingeschränkte Garantiebestimmungen

The unique serial numbers of the CE marked CI532 device are collected to facilitate follow-up with the clinics if required.

5 Justification for the design of the clinical investigation

An extended review of clinical performance data for CI532 device (Section 19) has identified limited hearing performance outcome data. Cochlear is already collecting post market clinical data with the ongoing CLTD5446, but is aiming to collect additional data from a wider subject population with this retrospective evaluation. Therefore the aim of this study is to establish more post-market hearing performance outcomes with CI532 to establish bench mark speech data for German hearing performance material for CI532 recipients.

6 Risks and benefits of the commercially available CI532 and clinical investigation

6.1 Anticipated clinical benefits

Within the scope of this study neither treatment nor special clinical interventions are planned. Therefore no anticipated clinical benefits for the patients are expected other than that this study will provide more insight in the benefits of CI treatment with CI532 as post-market follow-up. The CI532 Hazards Analysis and Routine post-market surveillance (PMS) will be updated with any new identified risks from this study.

6.2 Anticipated adverse device effects and risks related to the commercially available CI532, risks associated with participation in the clinical investigation and risk mitigation

Not applicable, because of this retrospective nature of this study. Patients are not exposed to any additional clinical investigational measurements beyond the clinical routine measures.

6.3 Risks associated with data protection

As precaution to avoid any risks associated with data protection the patient's identity and all information collected during the investigation will be kept strictly confidential and in accordance with EU data protection laws. Each participant's data will be given a unique code and the list of codes will be kept by the investigator as described in the data privacy section.

6.4 Risk-to-benefit rationale

In conclusion taking part in the study does not incur any risks for the participating patients.

The study aims to give insight in speech perception benefit at 6 months after switch on of CI532 and this will help clinicians in their routine clinical practice.

Given the above the potential benefits will outweigh the risks.

7 Objectives, hypothesis and Endpoints

7.1 Objectives

7.1.1 Primary Objective

To assess available speech understanding in quiet and in noise pre-operative (daily listening condition) and at 6 months post CI532 implantation (best aided conditions).

7.1.2 Secondary Objective

1. To compare available aided (daily listening condition) and unaided pure tone audiometric thresholds obtained before surgery and at 6 months after CI532 surgery
2. To get insight for available CI532 device characteristics (electrode impedances, NRT, MAP T and C levels) and patient characteristics (datalogging) (cdx files)
3. To assess subjective surgeon's opinion and clinical experience with CI532 via a questionnaire

7.2 Endpoints

7.2.1 Primary Endpoint

1. Change from pre-op (daily listening condition) baseline speech understanding in quiet and in noise at 6 months post-op (best aided conditions).
2. The proportion of the recipient cohort in percent examined showing post-operative improvement per test and listening condition.

7.2.2 Secondary Endpoint

1. Change from pre-op baseline aided (daily listening condition) and unaided thresholds at 6 months post-operative
2. Defined normative CI532 device characteristics (electrode impedances, NRT, MAP T and C levels) and patient characteristics (datalogging)
3. Combined subjective clinical experience and opinion about CI532 from surgeons

7.3 Hypotheses

7.3.1 Primary hypotheses of retrospective study

1. H₀: Speech understanding in quiet and in noise at the 6 months post-operative visit are equal with speech understanding in quiet and noise at the pre-operative evaluation visit
H₁: Speech understanding in quiet and in noise at the 6 months post-operative visit is better than speech understanding in quiet and noise at the pre-operative evaluation visit
2. H₀: The proportion of the recipient's cohort examined showing post-operative improvement per test and listening condition is below 80% for the 6 months post-operative visit.
H₁: The proportion of the recipient's cohort examined showing post-operative improvement per test and listening condition is $\geq 80\%$ (Dowell, Hollow & Winton, 2004) for the 6 months post-operative visit.

8 Design of the clinical investigation

8.1 General

The aim of this study is to assess hearing performance based on clinically available routine hearing measures to demonstrate changes from pre- to post-CI treatment for patients implanted with the CI532 cochlear implant in a German speaking cohort.

The study is multi-centric including five centres in Germany (Kiel, Erlangen, Frankfurt am Main, Freiburg, Hannover) to retrospectively gather bench mark hearing performance data of CI532 recipients. The centres have been chosen due to their experience with CI532 and the availability of hearing performance data with CI532.

The hearing performance data located in patient's hospital file will be pseudo-anonymized by the clinician and entered into the study database. Therefore no bias is expected and no corrective action on a potential bias is required.

The hearing performance data has been gathered as part of the routine clinical measurements pre-operatively and at 3 and 6 months post-operatively for speech understanding in quiet and in noise and for unaided and aided thresholds. In addition medical history, anomalies in terms of electrode placement and recipient's device characteristics will be collected. Surgeons with CI532 experience will be asked to retrospectively evaluate the handling and usability of CI532 during conducted surgeries.

A first data export will be conducted after 50 datasets have been entered to informally view the datasets per centre. Over the study period clinicians are asked to gradually enrol the CI532 recipient's based on available datasets. It is expected to enrol ≥ 150 datasets until end of the study.

8.2 Datasets for the commercially available CI532

The pre-operative datasets are dependent on the recipient's daily device use. This is dependent on the advice of the recipient's ENT practitioner or clinical routine and could consist of either: a) an unaided condition, b) hearing aid unilateral/bilateral, or c) unilateral CI. Preoperative device use and hearing performance will be collected and considered for analysis as the comparator to the postoperative hearing performance.

The post-operative best aided conditions are dependent on the clinical routine advice and could consist of: a) a contralateral hearing aid, b) unaided contralateral ear, or c) contralateral

CI. Evaluation of electrode placement and location in the scala, by e.g. imaging data, will be considered during postoperative hearing performance analysis.

8.3 Subjects

8.3.1 Inclusion Criteria

1. Ability to conduct adult hearing performance test material
2. Good German language skills to assess clinical hearing performance
3. All CI532 recipients assessed via routine clinical measurements at pre implant, and post implant intervals with available data records in hospital files.
4. Patients that have read understood and signed the PIC.

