8.4 Procedures

No product or procedure related training is required since we will collect pseudo-anonymised clinical follow-up data hearing performance data and device characteristic data exported from clinical software provided with this CE marked product. The clinics will be trained by the Clinical Project Manager how to pseudo-anonymise the clinical data.

The clinic will recruit patients by phone and or mail. Based on their clinical database they select patients that fulfil the inclusion criteria and will provide the Patient Informed Consent to these patients by mail. Potentially a follow-up call will be conducted by the clinic to answer open

questions from the recipient. After patients have signed the Patient Informed Consent they will send it back to the clinic.

After the clinic has received the signed Informed Consent the clinician enters the available hearing performance data from the recipient's hospital file into the electronic data capturing system in a pseudo-anonymized way (See section 15.2).

The device/patient characteristics will be collected through anonymized computer record files ("cdx") produced by the CustomSound software which is routinely used to fit the CI532 recipients. The cdx files will be pseudo-anonymized with a unique patient code and sent to Cochlear.

Study subjects did follow clinical routine treatment practices and this retrospective approach does not impact routine clinical treatment at the implanting centre.

The surgeon's questionnaire will be filled by at least one surgeon per site once that surgeon has achieved a minimum experience of ten (10) CI532 surgeries. This could be in the beginning or close to the end of the study based on the surgeon's experience with CI532. Completed paper surgeon's questionnaire will be shipped to the clinical project manager by regular mail for further handling and analysis.

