2 STATISTICS

A total of $n=150$ patients will be assessed. It is expected to enrol approximately 30 subjects per site to compensate the variability of speech understanding tests in noise across sites with a decent power per site.

At different points during follow-up data exports and interim analyses will be conducted. The first data export with available datasets is expected to take place in August 2016. Over the study period it is expected to gradually increase the number of available datasets and therefore also the number of datasets for following interim analyses. The final analysis is expected to cover 150 datasets by the end of July _____

The interim analysis will be of descriptive nature only to maintain the nominal type I error of 5%. Formal hypothesis testing will be confined to the final analysis.

The level of significance for all statistical tests is $\alpha=5\%$, 2-sided.

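### Language skill and test ability are judged by the clinic, with no set time point, when post-implant results are already on file, so eligibility can depend on the outcome and a borderline 80% claim could turn on it.

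*Protocol*

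**What the plan says.** Protocol 8.3.1 lists four inclusion criteria. The first is "Ability to conduct adult hearing performance test material" and the second is "Good German language skills to assess clinical hearing performance". Neither comes with a test, a cut-off, an assessor or a date at which it is judged. The third is "All CI532 recipients assessed via routine clinical measurements at pre implant, and post implant intervals with available data records in hospital files", so post-implant records must exist before a recipient can qualify. The fourth is signed consent.

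Protocol 8.4 says who applies them. Of the clinics it states: "Based on their clinical database they select patients that fulfil the inclusion criteria". Consent is then sought, and only after it is returned are the scores entered in the study database. Protocol 8.1 adds that "clinicians are asked to gradually enrol the CI532 recipient's based on available datasets".

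On bias, Protocol 8.1 notes that the clinician pseudo-anonymises the file data before entry and concludes: "Therefore no bias is expected and no corrective action on a potential bias is required".

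The SAP tests the second primary hypothesis with a two-sided exact binomial test against 80% (sections 2, 3 and 8.2), planned on 150 patients. Section 5 counts any gain over the pre-operative value as a response and an equal or worse value as a non-response.

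**The concern.** Criteria 1 and 2 are matters of judgement, made in retrospect by a clinic whose files already hold post-implant results. Nothing confines the judgement to what was known before surgery. A recipient who scores 0% before and after could readily be described as unable to do the test, and that recipient is a non-responder under SAP section 5.

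A recipient judged ineligible is never invited and never entered. Neither document provides for a screening log, a count of those not selected, or eligibility review without sight of the scores. No analysis of the entered data could reveal the loss. Pseudo-anonymisation protects identity after selection and does nothing about who is selected.

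If exclusions were related to change in score, the responder rate would be too high and the mean gain could be too. The study is meant to supply benchmark data (Protocol 3 and 5), so the benchmark would shift as well as the test.

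**Working it through.** **Inputs from the SAP.** n = 150, null rate 0.80, two-sided 5%, exact binomial (sections 2, 2.1 and 3). Table 3 gives rejection at ≤109 or ≥130, actual alpha 0.0411, and power 0.9279 at a true rate of 0.90.

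**Assumptions.** The documents give no number of exclusions, so k is assumed. Every excluded patient is taken to be a non-improver, which is the worst case.

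**Step 1: reproduce Table 3.** With X ~ Binomial(150, 0.80), P(X ≥ 130) = 0.0224 and P(X ≤ 109) = 0.0187, which sum to 0.0411. With a true rate of 0.90, the probability of rejection is 0.9279. Both agree with the SAP. A claim above 80% needs 130/150 = 86.7%.

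**Step 2: exclusions needed to reverse a failed result.** Start from x improvers among 150, remove k non-improvers, and retest x out of 150 − k. The two-sided p is 2·P(X ≥ x) under Binomial(150 − k, 0.80).

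| Unselected result | k needed | After exclusion | p |
|---|---|---|---|
| 129/150 (86.0%) | 1 | 129/149 | 0.049 |
| 128/150 (85.3%) | 3 | 128/147 | 0.034 |
| 127/150 (84.7%) | 4 | 127/146 | 0.037 |
| 126/150 (84.0%) | 5 | 126/145 | 0.041 |
| 125/150 (83.3%) | 6 | 125/144 | 0.045 |
| 122/150 (81.3%) | 10 | 122/140 | 0.037 |
| 120/150 (80.0%) | 12 | 120/138 | 0.045 |

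One to six exclusions are therefore enough only from 125 to 129 of 150, about 83–86%.

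**Step 3: chance of a claim over repeated studies.** This was computed in two ways. In (A), 150 candidates lose k non-improvers and the test is redone on the rest. In (B), 150 + k candidates lose k non-improvers, 150 are analysed, and the chance is P(X ≥ 130) under Binomial(150 + k, true rate).

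| k | True 80%, A / B | True 85%, A / B | True 90%, B |
|---|---|---|---|
| 0 | 2.2% | 33% | 92.8% |
| 1 | 3.7% / 3.4% | 42% / 41% | 95.3% |
| 3 | 5.9% / 7.2% | 51% / 56% | 98.2% |
| 5 | 12.9% / 13.4% | 68% / 70% | 99.4% |

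**Step 4: how much rests on perfect selectivity.** With 130 improvers among 156 (83.3%), the Clopper-Pearson 95% lower limit is 76.5%. Removing six non-improvers gives 130/150, with a lower limit of 80.2%, so the claim is made. If one of the six is an improver, the result is 129/150 with a lower limit of 79.4%, and the claim fails. If two are, it is 128/150 with 78.6%.

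**Step 5: smaller denominators.** The hypothesis is stated separately for each test and listening condition, and Protocol 9 says clinics use different noise tests, so one test may have fewer than 150 patients. With an assumed n = 60 and a true 80%, removing three non-improvers under (B) raises the chance of a claim from 1.2% to 9.4%. With an assumed n = 30 it rises from 1.1% to 18.2%.

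**The case against.** The strongest reply is that a poor performer is not the same as a non-improver. Any gain counts as a response under SAP section 5, so a low 6-month score after a still lower pre-operative one is a response. Poor German would depress both scores. Excluding low scorers could even remove improvers and lower the rate. This stands: only exclusions related to change push the rate up, and Steps 2 and 3 are worst cases.

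Second, a reader might infer that clinics do consult the scores, or that a handful of exclusions settles the 80% claim in general. The documents support neither. They never say that scores inform the judgement of language or ability. Criterion 3 speaks of all recipients, which points towards complete inclusion, and a Monitoring Plan that is not among these documents may contain checks. The reversal by one to six exclusions is confined to a narrow band of results. If the true rate is the planned 90%, an unselected count among 156 candidates falls where six such exclusions would matter (130 to 134) only about 6% of the time.

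Third, criterion 3 names post-implant intervals without specifying 6 months, so the presence of the 6-month score at selection is an inference. It is a likely one, because Protocol 8.1 describes routine measurements at 3 and 6 months.

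These points limit the size of the problem. They do not supply the missing time point. The wording of criterion 3 does not help either, because criteria 1 and 2 must be met as well.

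**Conclusion.** The concern holds as a weakness of design. Two subjective criteria without a time point are applied by the clinic when post-implant results are on file, and Protocol 8.1 dismisses bias on grounds that do not bear on selection. That outcome-dependent exclusion is possible follows from the text; that it happens does not.

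The size depends on two assumptions, the number excluded and that all of them are non-improvers. Under both, a failed claim could be reversed by one to six exclusions at an unselected rate of about 83–86%, while an observed 80% needs 12. At a true 80%, three to five exclusions raise the chance of a claim from 2.2% to about 6–13%. At the planned 90% the gain is small, from 92.8% to 98.2% with three exclusions. The effect on mean gain was not calculated. The point is worth correcting because the protection is nearly free and the loss could not be detected later.

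**What to change.** Add to Protocol 8.3.1 that criteria 1 and 2 are judged only from information recorded before surgery, that post-operative speech results may not be used to judge eligibility, and that a low or 0% pre-operative score does not by itself fail either criterion.

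Have each site log the CI532 recipients not included on criterion 1 or 2, with the reason, and report the count. Without the log, adherence to the rule cannot be checked.

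Delete the sentence in Protocol 8.1 that no bias is expected and no corrective action is required.

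Keep the language criterion. It should not be treated as met merely because a German test was given before surgery: criterion 3 already requires a pre-implant assessment, so that shortcut would make the language requirement redundant.

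The cost is a short log at each of the five sites and possibly a slightly less favourable result. No new measurements are needed.

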1.3 Hypotheses

1.3.1 Primary hypotheses of retrospective study

1. H_0 : Speech understanding in quiet and in noise at the 6 months post-operative visit are equal with speech understanding in quiet and noise at the pre-operative evaluation visit
 H_1 : Speech understanding in quiet and in noise at the 6 months post-operative visit is better than speech understanding in quiet and noise at the pre-operative evaluation visit
2. H_0 : The proportion of the recipient's cohort examined showing post-operative improvement per test and listening condition is below 80% for the 6 months post-operative visit.
 H_1 : The proportion of the recipient's cohort examined showing post-operative improvement per test and listening condition is $\geq 80\%$ (Dowell, Hollow & Winton, 2004) for the 6 months post-operative visit.

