5 DERIVED DATA

Derived data will include the binary response as a difference between baseline (pre-op) and 6 months post-operative visits, respectively. A response ($y=1$) will be defined as better speech understanding with respect to pre-op, a non-response ($y=0$) will be defined as a worse or equal speech understanding. In addition, paired differences of pre-op values vs. month 6 will be carried out.

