7 ANALYSIS POPULATIONS

ITT: the intention to treat population will comprise all patients with a baseline assessment.

PP: the per-protocol will include only patients with a non-missing assessment at pre-op and at visit 3 months or 6 months.

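### Recipients whose device failed, was explanted or was permanently abandoned before they were tested never count as non-responders in the 80% improvement hypothesis

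*Protocol*

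**What the plan says.** Inclusion criterion 3 (Protocol 8.3.1) admits "All CI532 recipients assessed via routine clinical measurements at pre implant, and post implant intervals with available data records in hospital files". Protocol 8.4 applies it at the selection step: "Based on their clinical database they select patients that fulfil the inclusion criteria".

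SAP section 5 constructs the responder variable: "Derived data will include the binary response as a difference between baseline (pre-op) and 6 months post-operative visits, respectively". Response is a better result than pre-op, and "a non-response ($y=0$) will be defined as a worse or equal speech understanding". Neither document gives a value to a recipient with no 6-month score, and neither mentions explantation, device failure or non-use in connection with this endpoint.

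The null of primary hypothesis 2 (SAP 1.3.1) is that the proportion "examined showing post-operative improvement per test and listening condition is below 80% for the 6 months post-operative visit". SAP 8.2 tests it with a one-sample binomial test against 80%.

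SAP section 7 defines two sets. For ITT, "the intention to treat population will comprise all patients with a baseline assessment". For PP, "the per-protocol will include only patients with a non-missing assessment at pre-op and at visit 3 months or 6 months". SAP 8.2 makes the ITT analysis a secondary sensitivity analysis, using a model with patient as random effect.

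Protocol 8.1 says that bias is not expected and needs no correction, reasoning from pseudonymised data entry. Protocol 16.1 adds a case report form question on whether incidents were reported to the sponsor, but does not link it to the endpoint.

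**The concern.** The eligibility rule and the response rule together keep a particular kind of treatment failure out of hypothesis 2. There are two routes:

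- A recipient whose device failed, was explanted or was abandoned, and who has no post-implant measurement, does not meet criterion 3.
- A recipient measured at 3 months whose device then failed, so that no 6-month test was done, is enrolled and sits in the PP set but has no pre-op to 6-month difference. The response variable is undefined, not zero.

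In both cases the absence of a score is caused by the outcome, so leaving these recipients out can only push the observed improvement rate up. The study is meant to supply benchmark data for CI532 recipients (Protocol sections 3, 5 and 8.1) and to help clinicians in routine practice (Protocol 6.4). A reader is likely to take a claim of at least 80% improved as a rate for people who receive the implant, when it is a rate for those who were tested after receiving it. Nothing planned would show how far apart the two are, since no count of recipients without a post-implant test is foreseen.

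**Working it through.** **Inputs from the documents.** n=150, P0=0.80, planning rate P1=0.90, rejection at 109 or fewer or at 130 or more, power 0.9279, actual alpha 0.0411 (SAP 2.1, Table 3); alpha 5% two-sided (SAP section 2).

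**Input not in the documents.** The share f of implanted recipients left out because of a device-related failure. No rate is given, so 1%, 2% and 5% are assumptions.

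**Step 1: the plan's own figures.** With X ~ Bin(150, p):
- P(X≥130 | 0.80) = 0.0224 and P(X≤109 | 0.80) = 0.0187, sum 0.0411.
- P(X≥130 | 0.90) + P(X≤109 | 0.90) = 0.9279.

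Both agree with Table 3. The power calculation is sound; the question is who is in the denominator.

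**Step 2: chance of a wrong claim about all recipients.** Let the true rate over all recipients, counting device-related failures as not improved, be exactly 0.80. If a share f, all failures, is left out, the rate among those tested is 0.80/(1−f). The chance of a claim above 80% is P(X≥130) at that rate.

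| f (assumed) | Rate among tested | P(X≥130), n=150 |
|---|---|---|
| 0 | 0.8000 | 2.2% |
| 1% | 0.80/0.99 = 0.8081 | 3.9% |
| 2% | 0.80/0.98 = 0.8163 | 6.4% |
| 5% | 0.80/0.95 = 0.8421 | 24.2% |

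**Step 3: how many added failures overturn a result.** Add k failures as y=0 to the 150 tested and compute the upper-tail p against 0.80, to be compared with 0.025.

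| Responders / n | k | Rate | Upper-tail p |
|---|---|---|---|
| 130/150 | 0 | 86.7% | 0.0224 |
| 130/151 | 1 | 86.1% | 0.0342 |
| 135/150 | 0 | 90.0% | 0.0008 |
| 135/156 | 6 | 86.5% | 0.0223 |
| 135/157 | 7 | 86.0% | 0.0339 |

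The first pair is the rejection boundary, where one extra non-responder is bound to matter. The second starts from the SAP's planning rate (0.90 × 150 = 135), where six can be absorbed and the seventh cannot.

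**Step 4: smaller denominators.** Hypothesis 2 is stated per test and listening condition, and noise tests differ by clinic (Protocol section 9), so some comparisons will have fewer than 150. As an illustration with n=60 (assumed), rejection starts at 55/60, and f=2% moves the upper tail from 1.2% to 2.5%. The direction is the same and the inflation smaller.

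**Step 5: does another analysis set recover these recipients?** The ITT definition is nominally wider than PP, but it is drawn from enrolled recipients, who have already passed criterion 3. For a recipient with only a 3-month score, the random-effects model uses that score; it does not turn the missing 6-month result into a non-response. Neither set counts the failure.

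**The case against.** The strongest reply is that the plan states its own target. The objective concerns available speech data, and hypothesis 2 concerns the recipients examined, so nobody is removed from the stated denominator. Counting an explantation as non-response is a different, composite estimand and hence a choice. This stands as a description of the primary test and is why that test need not change. It does not answer the benchmark use of the figure, or the Protocol's assurance about bias.

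A reader might infer that every recipient who failed with or gave up the device is ineligible. The documents do not support that. Criterion 3 asks for routine post-implant measurements; it does not ask for a speech score, a 6-month test or a working device. Thresholds are among the routine measures (Protocol 8.1), so a recipient with such records may qualify. A non-user can still be tested, because the best-aided condition may include a contralateral hearing aid or implant (Protocol 8.2).

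A reader might also infer that the 80% claim is fragile or materially inflated. The documents do not show this either. They give no failure rate, the illustration fixes the true rate at exactly 80%, and 130/150 is the boundary case: at the planning rate of 90% the chance of exactly 130 responders is about 4%. The planned 135/150 is fairly robust.

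Finally, the one-way direction holds for device-related failures only. Criterion 3 also shuts out recipients whose records are missing for other reasons, and the documents do not show which way those act.

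**Conclusion.** The point holds in a limited form. A recipient whose device failed, was explanted or was permanently abandoned before being tested never counts as a non-responder in hypothesis 2, either because criterion 3 bars entry or because SAP section 5 gives no response value without a 6-month score. For this group the direction is settled: the observed improvement rate can only go up. The size is unknown and may be small. The illustrative rise from 2.2% to between 3.9% and 24.2% rests on an assumed 1% to 5% left out, a true all-recipient rate of exactly 80% and a full 150 per comparison. A result near the rejection boundary would be sensitive to a single failure; one at the planning rate would not. Because this is a one-directional gap in a primary hypothesis and is cheap to examine, it should be addressed.

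**What to change.** Keep the primary analysis and make these changes:

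1. **SAP sections 5 and 8.2:** add a sensitivity analysis of hypothesis 2 that sets y=0 for any recipient with a pre-op score on the test in question and a documented device failure, explantation, re-implantation or permanent non-use before the 6-month test. Assign each to the test and listening condition used pre-op.
2. **Reporting:** each centre states how many of its CI532 recipients lacked a post-implant test, and why.
3. **Protocol 8.3.1:** extend criterion 3 to admit such recipients, with consent. If it is not extended, state that the 80% result applies only to recipients tested after implantation.
4. **Protocol 8.1:** remove the statement that bias is not expected.

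Cost: a protocol amendment with ethics committee notification (written approval if substantial, Protocol 14.2), a few more consent letters, some additional data fields, and possibly a slightly lower responder rate in the sensitivity analysis. If such failures prove few, that analysis will show that the claim is robust.
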